10.2 STATEMENT OF CONFIDENTIALITY

Individual patient medical information obtained as a result of this study is considered confidential and disclosure to third parties is prohibited with the exceptions noted below. Patient confidentiality will be ensured by using patient identification code numbers.

No subject names will be supplied to Boehringer Ingelheim or other responsible parties. Only the subject number and subject initials will be recorded on the CRF, and if the subject's name appears on any other document (e.g., medical chart), it must be obliterated before a copy of the document is supplied to Boehringer Ingelheim or other responsible parties. Study findings stored on a computer will be stored in accordance with local data protection laws.

Proprietary confidential information © 2019 Boehringer Ingelheim International GmbH or one or more of its affiliated companies

The investigator will maintain a personal subject identification list (subject numbers with the corresponding subject names) to enable records to be identified.

Treatment data may be given to the patient's personal physician or to other appropriate medical personnel responsible for the patient's welfare. Data generated as a result of the study need to be available for inspection on request by the participating physicians, the sponsor's representatives, by the IRB/IEC and the regulatory authorities. All personal information made available for inspection will be handled in strictest confidence and in accordance with local data protection laws.

11. MANAGEMENT AND REPORTING OF ADVERSE EVENTS/ADVERSE REACTIONS

11.1 DEFINITIONS OF ADVERSE EVENTS

Adverse event

An adverse event (AE) is defined as any untoward medical occurrence in a patient or clinical investigation subject administered a medicinal product and which does not necessarily have a causal relationship with this treatment. An adverse event can therefore be any unfavourable and unintended sign (e.g., an abnormal laboratory finding), symptom, or disease temporally associated with the use of a medicinal product, whether or not considered related to the medicinal product.

Adverse reaction

An adverse reaction is defined as a response to a medicinal product which is noxious and unintended. Response in this context means that a causal relationship between a medicinal product and an adverse event is at least a reasonable possibility. Adverse reactions may arise from use of the product within or outside the terms of the marketing authorization or from occupational exposure. Conditions of use outside the marketing authorization include off-label use, overdose, misuse, abuse and medication errors.

Serious adverse event

A serious adverse event is defined as any AE which

- results in death,
- is life-threatening,
- requires in-patient hospitalization, or
- prolongation of existing hospitalization,
- results in persistent or significant disability or incapacity, or
- is a congenital anomaly/birth defect

Life-threatening in this context refers to a reaction in which the patient was at risk of death at the time of the reaction; it does not refer to a reaction that hypothetically might have caused death if more severe.

Medical and scientific judgment should be exercised in deciding whether other situations should be considered serious reactions, such as important medical events that might not be immediately life threatening or result in death or hospitalization but might jeopardize the patient or might require intervention to prevent one of the other outcomes listed above. Examples of such events are intensive treatment in an emergency room or at home for allergic bronchospasm, blood dyscrasias or convulsions that do not result in hospitalization or development of dependency or abuse. Any suspected transmission via a medicinal product of an infectious agent is also considered a serious adverse reaction.

Adverse Event of Special Interest (AESI)

The term AESI relates to any specific AE that has been identified at the project level as being of particular concern for prospective safety monitoring and safety assessment within this study, e.g. the potential for AEs based on knowledge from other compounds in the same class.

No AESIs have been defined for this study.

11.2 ADVERSE EVENT AND SERIOUS ADVERSE EVENT COLLECTION AND REPORTING

The investigator shall maintain and keep detailed records of all AEs in their patient files.

Collection of AEs

The study design is of non-interventional nature and the study is conducted within the conditions of the approved marketing authorization. Sufficient data from controlled interventional trials are available to support the evidence on the safety and efficacy of the studied BI drug. For this reason the following AE collection and reporting requirements have been defined. **Only ADRs and AEs with fatal outcomes will be collected on the CRF due to the retrospective study design.** ADR is defined as that there is an actual causal relationship with Spiolto® on the medical chart.

The following must be collected by the investigator in the (e)CRF from signing the informed consent onwards until the end of the study:

- all ADRs (serious and non-serious),
- all AEs with fatal outcome,

The investigator carefully assesses whether an AE constitutes an ADR using the information below.

Causal relationship of adverse event

The definition of an adverse reaction implies at least a reasonable possibility of a causal relationship between a suspected medicinal product and an adverse event. An adverse reaction, in contrast to an adverse event, is characterized by the fact that a causal relationship between a medicinal product and an occurrence is suspected.

Medical judgment should be used to determine the relationship, considering all relevant factors, including pattern of reaction, temporal relationship, de-challenge or re-challenge, confounding factors such as concomitant medication, concomitant diseases and relevant history.

Arguments that may suggest a **reasonable causal relationship** could be:

- The event is **consistent with the known pharmacology** of the drug
- The event is known to be caused by or **attributed to the drug class**.
- **A plausible time to onset of the event** relative to the time of drug exposure.
- Evidence that the **event is reproducible** when the drug is re-introduced
- **No medically sound alternative etiologies** that could explain the event (e.g., preexisting or concomitant diseases, or co-medications).
- The event is typically **drug-related and infrequent in the general population** not exposed to drugs (e.g., Stevens-Johnson syndrome).
- An indication of dose-response (i.e., greater effect size if the dose is increased, smaller effect size if dose is diminished).

Arguments that may suggest that there is **no reasonable possibility of a causal relationship** could be:

- No plausible time to onset of the event relative to the time of drug exposure is evident (e.g. pre-treatment cases, diagnosis of cancer or chronic disease within days/weeks of drug administration; an allergic reaction weeks after discontinuation of the drug concerned)
- Continuation of the event despite the withdrawal of the medication, taking into account the pharmacological properties of the compound (e.g. after 5 half-lives).
Of note, this criterion may not be applicable to events whose time course is prolonged despite removing the original trigger.
- Additional arguments amongst those stated before, like alternative explanation (e.g. situations where other drugs or underlying diseases appear to provide a more likely explanation for the observed event than the drug concerned).
- Disappearance of the event even though the study drug treatment continues or remains unchanged.

Intensity of adverse event

The intensity of the AE should be judged based on the following:

Mild: Awareness of sign(s) or symptom(s) which is/are easily tolerated

Moderate: Enough discomfort to cause interference with usual activity

Severe: Incapacitating or causing inability to work or to perform usual activities

Pregnancy:

In rare cases, pregnancy might occur in a study. Once a subject has been enrolled into the study, after having taken BI drug taken for the disease in scope of the study, the investigator must report any drug exposure during pregnancy, which occurred in a female subject or in a partner to a male subject to the Sponsor by means of Part A of the Pregnancy Monitoring Form. The outcome of the pregnancy associated with the drug exposure during pregnancy must be followed up and reported by means of Part B of the Pregnancy Monitoring Form.

In the absence of a reportable AE, only the Pregnancy Monitoring Form must be completed, otherwise the NIS AE form is to be completed and forwarded as well within the respective timelines.

Expedited Reporting of AEs and Drug Exposure During Pregnancy

The following must be reported by the investigator on the NIS AE form from signing the informed consent onwards until the end of the study:

| Type of Report | Timeline |
|--|-----------------------------|
| All SADRs associated with the Spiolto® | immediately within 24 hours |
| All AEs with fatal outcome in patients exposed to Spiolto® | immediately within 24 hours |
| All non-serious ADRs associated with the Spiolto® | 7 calendar days |
| All pregnancy monitoring forms | 7 calendar days |

Proprietary confidential information © 2019 Boehringer Ingelheim International GmbH or one or more of its affiliated companies

The same timelines apply if follow-up information becomes available for the respective events. In specific occasions the Investigator could inform the Sponsor upfront via telephone. This does not replace the requirement to complete and fax the NIS AE form.

Information required

For each reportable adverse event, the investigator should provide the information requested on the appropriate (e)CRF pages and the NIS AE form.

Reporting of related Adverse Events associated with any other BI drug

The investigator is encouraged to report all adverse events related to any BI drug other than the Spiolto® according to the local regulatory requirements for spontaneous AE reporting at the investigator's discretion by using the locally established routes and AE report forms. The term AE includes drug exposure during pregnancy, and, regardless of whether an AE occurred or not, any abuse, off-label use, misuse, medication error, occupational exposure, lack of effect, and unexpected benefit.

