6. MILESTONES

| Milestone | Planned Date |
|-------------------------------------|---------------------|
| IRB/IEC approval | 31 July 2019 |
| Start of data collection | 01 August 2019 |
| End of data collection | 30 November 2019 |
| Registration in the EU PAS register | 31 July 2019 |
| Final report of study results: | 31 January 2020 |

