9.2.2 Study population

The data will be retrospectively abstracted from the medical chart after eligibility assessment. Eligible patients will be categorized into the cohort A (patients treated with Tio + Olo), B (patients treated with other LABA/LAMA therapy), and C (patients treated with LAMA therapy).

Inclusion criteria

Patients who fulfil **ALL** the following criteria are included.

1. Patients who diagnosed with COPD who were prescribed with LABA/LAMA (FDC or free combo) as a new initiation or switching from other therapy (i.e., single/dual/triple), or newly receiving LAMA treatment for 3 months at least prior to 30 June 2018
2. Male or female patients ≥ 40 years of age

Exclusion criteria

Patients who meet the following criterion are not included.

1. Patients with documented diagnosis of bronchial asthma, asthma-COPD overlap syndrome (ACOS), bronchiectasis, cystic fibrosis, or lung cancer

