9.2.3 Study visits

The abstracted data will be recorded on the case report form (CRF). **Table 1** shows the collected data at different retrospective period of the medical chart.

Table 1 Data collection schedule

| Variables | Time points | Eligibility assessment | Data collection retrospectively | | |
|----------------------------------|-------------|------------------------|---------------------------------|-------------------------|--------------------------------------|
| | | | Before the index date | Index date [#] | 1-year follow-up period [†] |
| Eligibility assessments | X | | | | |
| Demographics ¹ | | | | X* | |
| Diagnosis of COPD ² | | | | X* | |
| Smoking status ³ | | | | X* | |
| Comorbidity ^{4, §} | | X [◊] | X | X | |
| COPD assessments [‡] | | | | | |
| CAT ⁵ | | X ^Δ | X | X | |
| mMRC ⁶ | | X ^Δ | X | X | |
| Examinations [‡] | | | | | |
| Spirometry data ⁷ | | X ^Δ | X | X | |
| Eosinophils | | X ^Δ | X | X | |
| Records [‡] | | | | | |
| Acute exacerbations ⁸ | | X ^{&} | X | X | |
| Hospital admissions ⁹ | | X ^{&} | X | X | |
| Treatments | | | | | |

| Variables | Time points | Eligibility assessment | Data collection retrospectively | | |
|--|-------------|------------------------|---------------------------------|-------------------------|--------------------------------------|
| | | | Before the index date | Index date [#] | 1-year follow-up period [†] |
| Related to COPD ^{10, \$} | | | X ^{11, ♦} | X | X |
| Related to comorbidities ^{12, \$} | | | X [◊] | X | X |
| Rescue treatments ^{13, ‡} | | | X [◊] | X | X |
| Oxygen therapy ^{14, \$} | | | X [◊] | X | X |
| Others ^{15, \$} | | | X [◊] | X | X |

[#]Not later than 30 June 2018; defined as the date of COPD patients in the cohort A and B starting using LABA/LAMA therapy regardless of new initiation or switching from other single/dual/triple treatment, or the date of the patients in the cohort C starting using LAMA treatment

[†]Not later than 1 year after the index date

^{*}The data nearest to the index date will be collected.

[◊]The data 6 months before the index date will be documented.

^{\$}The data will be collected every 6 months (allowed window: ± 1 month).

[‡]All available data on the medical chart will be recorded.

[△]The data nearest to the index date will be collected as the **Baseline**.

[&]The data/events ever since patients started receiving LABA/LAMA or LAMA therapy will be collected (maximum: trace back to 1 year before the index date).

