10.1 STUDY APPROVAL, PATIENT INFORMATION, AND INFORMED CONSENT

This study will be initiated only after all required legal documentation has been reviewed and approved by the respective Institutional Review Board (IRB)/Independent Ethics Committee (IEC) and Competent Authority (CA) according to national and international regulations. The same applies for the implementation of changes introduced by amendments.

Prior to the start of data collection in the study, written informed consent must be obtained from each patient (or the patient's legally accepted representative) if requested by IRBs or the local regulatory organization. Each signature must be personally dated by each signatory and the informed consent and any additional patient-information form retained by the investigator as part of the study records. A signed copy of the informed consent and any additional patient information must be given to each patient or the patient's legally accepted representative.

The patient must be informed that his/her personal study-related data will be used by Boehringer Ingelheim in accordance with the local data protection law. The level of disclosure must also be explained to the patient.

The patient must be informed that his/her medical records may be examined by Quality Medicine auditors appointed by Boehringer Ingelheim, by appropriate IRB IEC members, and by inspectors from regulatory authorities.

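### Section 11.2 opens the adverse-event window at signed consent, so read literally it misses every patient's follow-up year and has no start where consent is not requested

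*Combined protocol and SAP*

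**What the plan says.** Section 11.2 states the scope first: "Only ADRs and AEs with fatal outcomes will be collected on the CRF due to the retrospective study design". It then defines an ADR by a causal relationship with Spiolto that is recorded in the medical chart. Both statements point to events already in the chart.

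The next instruction sets the CRF collection window for all ADRs and all fatal AEs: "from signing the informed consent onwards until the end of the study". Under the expedited-reporting heading the same window is repeated for reports made "on the NIS AE form from signing the informed consent onwards until the end of the study". Pregnancy monitoring forms are listed under that second window too.

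Elsewhere in the protocol:
- The Table 1 footnotes (section 9.2.3) fix the index date as "Not later than 30 June 2018" and the follow-up period as "Not later than 1 year after the index date".
- Section 9.1 ends chart review at death or at one year from index, if earlier.
- Section 6 plans "IRB/IEC approval | 31 July 2019" and a start of data collection on 1 August 2019. The Abstract gives July 2019 for that start.
- Section 10.1 allows the study to begin only after approval. It places written consent before data collection, but only "if requested by IRBs or the local regulatory organization".

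**The concern.** A window that opens at signature suits a prospective study, where consent precedes exposure. Here exposure and follow-up are over before the study can approach anyone. If sites apply the sentence as a rule about when events occur, the ADRs and fatal AEs of the follow-up year are out of scope, although the preceding sentences plainly mean to collect them.

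Fatal events are the clearest case. A patient who died during follow-up cannot sign afterwards, and a representative's signature, which section 10.1 permits, would still postdate the death.

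If some of the roughly 12 sites abstract past events and others do not, the listings will not be comparable. A report that none were collected could then be taken to mean that none occurred. The 24-hour and 7-day reporting timelines also lack a stated trigger for an event that happened a year or more before anyone read the chart.

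**Working it through.** The plan gives no figure to reproduce. The check is calendar arithmetic on its own dates.

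**Inputs**
- Latest index date: 30 June 2018 (Table 1 footnote).
- Longest follow-up: 1 year (Table 1 footnote, section 9.1).
- Planned ethics approval: 31 July 2019 (section 6).
- Planned start of data collection: 1 August 2019 (section 6) or July 2019 (Abstract), taken as 1 July 2019 at the earliest.
- Consent, where requested: after approval and before data collection (section 10.1).

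**Latest end of follow-up** = latest index date + 1 year = 30 June 2018 + 1 year = 30 June 2019.

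**Gap** = milestone date − latest end of follow-up:
- to ethics approval: 31 July − 30 June 2019 = 31 days;
- to data collection per section 6: 1 August − 30 June 2019 = 32 days;
- to the earliest reading of the Abstract: 1 July − 30 June 2019 = 1 day.

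**Stricter index date.** Inclusion criterion 1 (section 9.2.2) speaks of "newly receiving LAMA treatment for 3 months at least prior to 30 June 2018", with the same cut-off in section 9.1 for LABA/LAMA. If the three months must be complete by then, the latest index date is about 30 March 2018 and follow-up ends about 30 March 2019. The three gaps become 123, 124 and 93 days.

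Every gap is positive, so the overlap between the consent-onward window and any patient's follow-up year is 0 days on every planned date. The 1-day figure is the smallest gap. It depends on the Abstract's date, which conflicts with section 6 and, if early July is meant, with section 10.1's rule that nothing starts before approval.

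**Does another section repair it?** Table 1 has no row for ADRs or AEs. The list of data to be taken from source documents (section 9.10.2.1) does not name them. Section 11.2 is the only text that sets an event window.

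**If consent is not requested.** The window is defined by a signature that never takes place. That is an undefined start, a separate failure from zero overlap.

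**Size of what is exposed**
- Spiolto ADRs: about 300 Tio + Olo patients (section 9.5) × at most 1 year = at most about 300 patient-years. The note under Table 2 assumes about 2 patient-years each, but the follow-up rule allows at most 1, so 1 is used here.
- Fatal-AE records: the CRF list has no product restriction, so all cohorts count, about 1,800 patients. The Spiolto restriction on fatal AEs appears only in the expedited-reporting table.

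These are patients and exposure time, not event counts. The documents give no ADR or death rate.

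**The case against.** The strongest reply is grammatical. In both places the phrase can govern when the investigator collects or reports, not when the event occurs. Where consent is required, collecting could not lawfully start sooner anyway, and the bold sentence just before supports that reading. On it, past events in the chart are in scope and no window is empty. This is a fair reading and probably the intended one. But the text does not say so, the other reading is at least as natural to a site used to prospective studies, and neither reading gives a start where consent is not requested.

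Three stronger inferences are tempting, and the documents do not support them:
- *The ADR and fatal-event listing would be empty.* Even on the literal reading, events after consent and up to the end of the study are still collected. What drops out is the follow-up year.
- *Deaths would be lost.* The date of death ends follow-up under section 9.1, so it has to be known regardless of section 11.2. What could be missing is the fatal-AE record.
- *About 300 patient-years measures both event types.* It fits Spiolto ADRs only.

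The reply that the impact is limited also stands. The study is not a PASS, safety is neither a primary nor a secondary outcome, and no analysis in section 9.7.1 uses ADR data.

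**Conclusion.** Wrong as written. Taken literally, the window stated twice in section 11.2 has 0 days of overlap with any patient's follow-up and contradicts the retrospective, chart-based intent stated in the same section. Where consent is not requested, it has no start. Because the wording also admits a reading under which past events are in scope, the practical risk is inconsistent application across sites rather than certain loss.

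Exposed are Spiolto ADRs in about 300 patients and CRF fatal-AE records in about 1,800. Time to first exacerbation and the secondary outcomes are untouched.

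The conclusion rests on the planned dates. Overlap would require approval and consent before 30 June 2019, against the protocol's own milestone, and a later actual start would widen the gap.

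**What to change.** Reword section 11.2 in both places, the CRF collection list and the expedited-reporting paragraph:
1. State that ADRs and fatal AEs documented in the chart between the index date and the end of follow-up (death, or one year from index if sooner) are in scope whether or not a consent form is signed. Section 10.1 continues to decide whether consent must precede abstraction.
2. Keep the existing post-consent collection and reporting and the pregnancy-form requirement. Replacing the window outright would drop later events and leave the pregnancy forms without a reporting period.
3. State that the existing timelines in the reporting table run from the moment the event is identified in the chart.

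The cost is a wording amendment and a little extra abstraction from charts already under review. Timing matters: this version is dated 25 November 2019, five days before the planned end of data collection on 30 November, so charts already abstracted may need a short re-check for ADRs and fatal-AE records.
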